#### Phase I: Screening

At screening all prospective subjects will sign the informed consent. A copy of the signed informed consent will be given to each participant. At the time of admission to the study, the patient's current treatment provider, if any, will be consulted, with the patient's permission, about the patient's participation in the study. After informed consent is obtained, patients will be eligible to be screened for inclusion in the study.

Screening will consist of several activities designed to validate that patients are suffering from bipolar illness, are currently in the depressed phase, and have been depressed in the current episode for at least four weeks but not longer than three years. The main screening tool will be the Mini International Neuropsychiatric Interview (M.I.N.I.) (Sheehan 1998). The Montgomery-Asberg Depression Scale (MADRS), the Young Mania Rating Scale (YMRS) and the Clinical Global Impression of Severity of Illness (CGI-S) rating will be done to confirm the patients' depression level and the absence of mania. As well, patients will be evaluated for the presence of any medical or psychiatric conditions that would either make it unsafe for them to participate in the trial (i.e., an unstable medical condition) or confound evaluation of the course of their bipolar condition (i.e., the presence of psychosis, substance abuse, or an eating disorder). Please see inclusion and exclusion criteria for specific qualifying parameters. When all inclusion criteria have been met and none of the exclusion criteria are present, patients are eligible to enter Phase II. They will be kept on mood stabilizing agents but will be tapered off of antidepressants. . As part of this initial evaluation, the study physician will evaluate the course of each subject's illness to determine the optimal medications to use during the course of TMS. If the subject, the referring physician or the study physician feels that it would be unsafe or unwanted to stop the antidepressant medication, the subject will be dropped from study participation and returned to routine clinical care. The course of TMS treatment will not start until two weeks after the antidepressant has been completed. This phase will last 1 to 28 days in order to accommodate possible changes in medication.

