### **Inclusion and Exclusion Criteria – Phase II**

Patients must meet fulfill all of the following inclusion criteria in order to enter Phase II of the study:

1. Must be at least 18 years old.

2. Must meet **DSM-5** criteria for bipolar (either I or II) depression by clinical interview and M.I.N.I. The duration of the current depressive episode must be at least 4 weeks and no longer than 3 years in length.
3. Should have a MADRS score of at least 20 at screening, an YMRS score of less than 12 and a CGI score of at least 4.
4. Must have signed the informed consent document and have a level of understanding sufficient to provide informed consent and to communicate with the investigator and site personnel.
5. Must be on a mood stabilizer acceptable to the study physician which is consistent with their diagnosis. The mood stabilizer must be at a stable dose for at least four days before starting TMS treatment.
6. If female of childbearing potential, patients must
  - a) have a negative urine pregnancy test at screening, and
  - b) not be nursing or planning a pregnancy, and
  - c) be on a medically acceptable method of birth control acceptable to the principal investigator.

Choices of contraception that meet the study requirements are

- Intrauterine device
- Hormonal contraception (estrogen-containing birth control pills, Vaginal ring, patch, injections or implants)
- Latex condom with spermicide
- Diaphragm with spermicide
- Cervical cap with spermicide

Females of childbearing potential who are abstinent can enroll in the study.

Patients will *not* be enrolled in Phase 2 of the study if they meet any of the following exclusion criteria:

1. May not be directly affiliated with Sheppard Pratt Clinical Research Programs or be immediate family of Research Programs personnel.
2. Must not have another primary Axis I diagnosis.
3. The subject must not have stopped an antidepressant less than two weeks before starting TMS treatment or unable to discontinue antidepressant therapy.
4. Should have no previous history of psychosis or substance dependence or abuse within the six months prior to Screening

5. Presence of an Axis II disorder felt by the investigator to potentially interfere with study compliance would exclude a potential participant.
6. Should not have prior intolerance of TMS or significant lack of response to adequate trials of TMS.
7. Should not have a lifetime history of lack of response to ECT or VNS.

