### **Patient Withdrawal**

Patients will be told verbally and in the informed consent that they have the right to withdraw from the study at any time without prejudice or loss of benefits to which they are otherwise entitled.

The investigator may discontinue a patient from the study for the following reasons:

- Non-compliance with 5-day TMS treatment schedule. Patients must complete at least 4 consecutive days of treatment per week.
- It is the judgment of the investigator that the patient may be at risk for suicide
- The patient has rated a “yes” to question 4 or question 5 on the C-SSRS “Since Last Visit” version
- Patient meets relapse criteria (MADRS score  $\geq$  20 for two consecutive weeks
- Onset of manic or mixed symptoms
- Pregnancy
- Intercurrent illness, adverse event or any other reason concerning the well-being of the patient.

Patients who voluntarily withdraw from the study or who are discontinued from the study will be asked to complete an early termination visit. The early termination visit will be done one week after study withdrawal. A MADRS and CGI will be performed by the investigator. Patients will be referred back to their treating psychiatrist for standard clinical care.

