### Treatment Compliance

The goal of treatment is: 1) at least four treatments per week and 2) no more than 3 consecutive days without a treatment. Patients unable to adhere to this schedule will be discontinued.

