## **Efficacy Measures and Safety Evaluations**

### Primary Efficacy Measure:

- Montgomery-Asberg Depression Rating Scale (MADRS)

Change from baseline to endpoint in MADRS total score will be the primary efficacy measure. The MADRS is a widely used rating scale for severity of mood related symptoms (Montgomery and Asberg, 1979). The scale consists of 10 items and ranges from 0 to 60. Higher scores denote more severe symptoms. The MADRS score (as opposed to the HAMD) is more sensitive to detect changes in the psychic rather than physical symptoms of depression.

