### **Statistical Methods**

- Sample Size

We are looking to collect sufficient data to demonstrate the efficacy and safety of TMS in bipolar depression. As this is an open label trial we will aim to treat 30 patients to achieve a reasonable sample size.

- Primary Efficacy Analysis

The primary outcome measure will be the percentage of patients who respond or remit after 30 to 35 treatments. We will subdivide patients based on the diagnosis of either bipolar I or bipolar II to compare effectiveness between those groups.

The other primary outcome will be the percentage of patients who meet criteria for onset of manic symptoms based on the YMRS. The patients will also be separated based on their diagnostic category.

- Secondary Efficacy Analysis

We will also look at the HAM-D and CGI to see the percentage of patients meeting response criteria.

For the patients meeting remission criteria, we will calculate the number of treatments required to achieve remission. Patients who only meet response criteria will be treated for 30 to 35 sessions.

Responders and remitters will also be followed for six months after the final treatment to see the durability of response. Percentage of patients' meeting relapse criteria will be calculated.

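### Two different primary efficacy outcomes are named, and the response percentage has no stated rule for patients discontinued during treatment

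*Combined protocol and SAP*

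**What the plan says.** Two sections define the primary efficacy outcome. Under Primary Efficacy Measure the plan states "Change from baseline to endpoint in MADRS total score will be the primary efficacy measure". Under Statistical Methods it states "The primary outcome measure will be the percentage of patients who respond or remit after 30 to 35 treatments". The only other primary outcome in Statistical Methods is the safety one, onset of manic symptoms on the YMRS. MADRS change does not appear there.

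Study Overview and the Phase II section define response as a MADRS fall of at least 50% and remission as a score below 10. Treatment stops at remission, and Statistical Methods adds "Patients who only meet response criteria will be treated for 30 to 35 sessions".

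On discontinuation, Patient Withdrawal lists reasons that include missed sessions, suicide risk, manic or mixed symptoms and adverse events. Treatment Compliance says "Patients unable to adhere to this schedule will be discontinued". Patient Withdrawal also says "Patients who voluntarily withdraw from the study or who are discontinued from the study will be asked to complete an early termination visit". That visit falls one week later, and at it "A MADRS and CGI will be performed by the investigator".

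On the starting score, the entry criterion reads "Should have a MADRS score of at least 20 at screening". Of the screening phase, which includes any antidepressant taper, the plan says "This phase will last 1 to 28 days in order to accommodate possible changes in medication".

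**The concern.** A mean change and a proportion are different summaries, with different analyses and possibly different messages. If both carry the primary label, either can be put forward once the data are known.

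The percentage is itself not fully defined. It is tied to having had 30 to 35 treatments. A patient discontinued in Phase II for side effects, activation or missed sessions does not reach that point, so on a literal reading that patient leaves the calculation. Such patients are unlikely to have done as well as completers, so leaving them out would push the rate up.

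The trial has one arm, no success threshold and no stated basis for its sample size. The response percentage is therefore the efficacy answer, and its denominator and reference score should be fixed before anyone sees results.

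**Working it through.** **1. The two definitions side by side.** Primary Efficacy Measure gives a continuous outcome, MADRS change from baseline to endpoint. Statistical Methods gives a binary one, response or remission. Nothing links or ranks them, and no analysis of the first is described.

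**2. The plan's own figure.** The Background section reports a routine-care series of 45 patients: 4 stopped for side effects, 5 finished with another provider, and 2 had incomplete data.
- Completers: 45 − 4 − 5 − 2 = 34.
- Response: 26/34 = 76.5%, which matches the stated figure. The denominator is completers.

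**3. The same 26 responders over other denominators** (exact Clopper-Pearson 95% intervals):

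| Denominator | Rate | 95% CI |
|---|---|---|
| Completers | 26/34 = 76.5% | 58.8 to 89.3 |
| Plus the 4 side-effect stops, as failures | 26/38 = 68.4% | 51.3 to 82.5 |
| All treated, all 11 non-completers as failures | 26/45 = 57.8% | 42.2 to 72.3 |

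The last row is a conservative bound, because the 5 transferred patients and the 2 with incomplete data are not known failures.

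**4. Shift at planned size.** Let c be the completer response rate and w the fraction withdrawn. If all withdrawn patients count as failures, the all-treated rate is c(1 − w), so the shift is c × w. Take c = 0.7647 (26/34, assumed to carry over).
- w = 4/45, the series' side-effect stop rate: 0.7647 × 0.0889 = 6.8 points, giving 69.7% of all treated.
- w = 5% (assumed): 3.8 points.
- w = 20% (assumed): 15.3 points.

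Statistical Methods aims for 30 patients; Study Population adds 20 at the second site. In whole patients at the 4/45 rate:
- 30 treated: 21/27 = 77.8% of completers against 21/30 = 70.0% of treated (50.6 to 85.3).
- 50 treated: 35/46 = 76.1% against 35/50 = 70.0% (55.4 to 82.1).

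The shorter arms of those two intervals are 85.3 − 70.0 = 15.3 and 82.1 − 70.0 = 12.1 points. The 6.8-point shift lies inside both; the 15.3-point end of the assumed range does not lie clearly inside either.

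**5. Baseline, with assumed scores.** Suppose a patient scores 30 at screening, 26 just before treatment and 14 at the end.
- From screening: (30 − 14)/30 = 53.3%, a responder.
- From the pre-treatment score: (26 − 14)/26 = 46.2%, a non-responder.

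This shows that the choice can reclassify a patient. It does not estimate how many would be affected.

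**The case against.** The strongest reply is that this is a small open-label study with no test or threshold, and that the likely denominator effect is smaller than its sampling error. The second part is right at the 4/45 stop rate. However, a confidence interval around a completer rate describes chance variation only and gives no sign of a one-directional bias. The plan also says it aims to demonstrate efficacy, so the headline rate will be read as evidence.

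Four stronger readings are tempting, and the documents do not support them.
- A reader might infer that the denominator explains more than half of the series' lead over the sponsor's 62% unipolar rate, since 76.5 − 62 = 14.5 points becomes 68.4 − 62 = 6.4. The denominator behind 62% is not given and may also be completers, so no like-for-like margin can be drawn. The planned unipolar comparison concerns time to response, not this rate.
- A reader might infer an intention to report completers only. The Background section openly lists all 11 exclusions, and nothing says what will be done in this trial.
- A reader might infer that no baseline exists anywhere. The schedule table is not shown and may label one, so the point is limited to the visible text. A visit schedule would not be expected to settle the denominator or which outcome is primary.
- A reader might infer that early remitters are excluded, or that the 30-session and 35-session statements conflict. Statistical Methods plainly means remitters to count, and the extra sessions can be read as a discretionary extension of a standard course.

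It is also fair to say that counting withdrawals as failures is one choice among several. The defect is that the plan states no choice.

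**Conclusion.** The point holds. The plan names two primary efficacy outcomes without ranking them. The one it analyses is worded so that patients discontinued in Phase II fall out, and no visible rule brings them back, although a MADRS is requested from them. This is a fault in the definition as written, not just missing detail, and it should be corrected before data are examined. The baseline gap is secondary and depends on what the schedule table contains.

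The likely size is about 6.8 points upward at a 4/45 stop rate, or 3.8 to 15.3 points if 5% to 20% withdraw. These figures assume that the routine-care completer rate carries over and that every withdrawn patient is a failure. A withdrawn patient who had already responded would make the shift smaller.

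**What to change.** In Primary Efficacy Measure and Statistical Methods, name one primary efficacy outcome: the percentage of all patients receiving at least one TMS session who have a MADRS fall of at least 50%, or a score below 10, at the end of Phase II. The end of Phase II is the remission stop or the last session given. Measure the fall from the last MADRS before the first session, report an exact 95% confidence interval, and make MADRS change secondary.

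Add these scoring rules, for this analysis only:
- Patients discontinued during Phase II before a remission stop or course completion are non-responders. This includes those discontinued for manic or mixed symptoms, whatever their MADRS that week.
- A patient who finishes treatment without a final-week MADRS is scored by the last weekly Phase II MADRS.
- Withdrawal or relapse in Phase III does not alter acute response status.

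Report two sensitivity results: (a) discontinued patients scored by their last weekly or early-termination MADRS, and (b) the completer rate, labelled as such.

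Phase III entry and clinical management stay as they are. The cost is wording and a little more analysis, using ratings the plan already collects. The sponsor should confirm that a pre-treatment and a final-week MADRS are scheduled. The headline rate may be less favourable than a completer rate, and a patient who responds and is then discontinued counts as a failure in the primary result; result (a) shows how much that matters.

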## Aims and Hypotheses

The primary aims of this study are:

1. To provide clear open-label evidence that a standard course of TMS therapy can be effective for patients who have a diagnosis of bipolar depression and are currently on mood stabilizing medication.
2. To investigate the safety of TMS in a population at risk for activation from neuromodulation. In particular to observe if these patients are at risk for changing from a depressive state to a mixed or manic state.

Specific Hypotheses are that:

1. TMS will provide effective antidepressant treatment in patients with bipolar depression both type I and II.
2. TMS will show a shorter time to response in bipolar depressed patients compared with the available data in unipolar depressed patients.
3. TMS can be safely given in bipolar depression without inducing a manic or mixed episode switch in patients who are receiving adequate concurrent mood stabilizing medication.

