### **Study Overview and Hypotheses**

We propose to screen patients with bipolar depression I or II, who are already on acceptable mood stabilization. They may or may not be on antidepressants at the time of screening but subjects on antidepressants would be taken off them before completing the screening phase. Those patients who have a depression of at least moderate severity without significant symptoms of activation or mania will be started on a course of open label TMS treatment of up to 35 sessions. Safety and efficacy assessments will be done weekly. Patients will complete a course of treatment when they meet remission criteria (MADRS score < 10) or at the end of 30 treatments, whichever comes first. Patients who are still judged to be improving between treatment 25 and treatment 30 will be eligible to complete up to five additional treatments as the discretion of each site's principal investigator.

Patients who meet response criteria (MADRS score decreases by at least 50%) will complete the full course of 30 to 35 TMS sessions. Patients will be withdrawn for safety concerns, particularly the onset of activation suggestive of mania or a mixed state.

Patients who meet response or remission criteria will be followed monthly for up to six months to evaluate the durability of response. They will be on standard mood stabilizing medications and psychotherapy per their clinician's discretion.

The primary study hypotheses are:

1. TMS will provide effective antidepressant treatment in patients with bipolar depression both type I and II.
2. TMS will show a shorter time to response in bipolar depressed patients compared with the available data in unipolar depressed patients.
3. TMS can be safely given in bipolar depression without inducing a manic or mixed episode switch in patients who are receiving adequate concurrent mood stabilizing medication

The secondary hypothesis is:

1. The majority of treatment responders will show adequate durability of response with remitters showing better durability.

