### **Study Population**

It is estimated that up to approximately 30 patients will participate in the study at the Sheppard Pratt site with 20 additional patients enrolling at the Mayo Clinic Rochester site. Patients must have Bipolar I or Bipolar II depression as defined by the Diagnostic and Statistical Manual of Mental Disorders (DSM-5 criteria) and be taking a mood stabilizer acceptable to the principal investigator. They will not be allowed to take antidepressant medication. Their depression must be at least moderate in severity without significant symptoms of activation or mania.

Patients treated may come from the Retreat assisted living, outpatient services, outpatient practices of local psychiatrists, the Sheppard Pratt day hospital, or inpatient units. Patients enrolled at Mayo Clinic will come from their Mood program, Mood Clinic, Inpatient practice and the community. It is unlikely that current inpatients will qualify for this study as most of them will have co-morbidities, psychotic symptoms or mixed presentations which would exclude them.

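### Bipolar I and II are compared on response percentages with no stated interval or adjustment, while MADRS change goes unused; a baseline-adjusted MADRS analysis is modestly more precise and needs no new data

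*Combined protocol and SAP*

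**What the plan says.** Hypothesis 1 (Aims and Hypotheses, repeated in Study Overview and Hypotheses) is that "TMS will provide effective antidepressant treatment in patients with bipolar depression both type I and II".

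Statistical Methods, Primary Efficacy Analysis, sets a binary outcome: "The primary outcome measure will be the percentage of patients who respond or remit after 30 to 35 treatments". It continues: "We will subdivide patients based on the diagnosis of either bipolar I or bipolar II to compare effectiveness between those groups". No estimator, test, interval, covariate, site term or group size follows.

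The Primary Efficacy Measure section names a continuous outcome instead: "Change from baseline to endpoint in MADRS total score will be the primary efficacy measure". Statistical Methods does not mention it again.

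The sample size is given in two ways. Statistical Methods says "we will aim to treat 30 patients to achieve a reasonable sample size". Study Population expects that "approximately 30 patients will participate in the study at the Sheppard Pratt site with 20 additional patients enrolling" at a second site. The expected number of patients of each type is not given.

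Two other provisions bear on the comparison. Treatment ends early when MADRS falls below 10 (Phase II). The mood-stabiliser requirement is stricter for bipolar I than for bipolar II (Rationale for Use of Mood Stabilizers).

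**The concern.** A comparison between diagnoses sits inside the primary efficacy analysis, but it is tied to a yes/no outcome and has no stated measure of uncertainty. Cutting MADRS at a 50% fall discards information from a score that is already rated weekly and already called primary. Without an interval, two similar percentages in small groups can be taken as showing that the types respond alike, and two dissimilar ones as showing that they do not. Because the method is left open, it can also be chosen after the data are seen. At stake is how far the report can go beyond each type's own response rate to a statement about the difference between types.

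**Working it through.** **Inputs from the documents.** N = 30 (Statistical Methods) or 30 + 20 = 50 (Study Population). The Background gives a response rate in completers from the clinic's own database: 45 − 4 − 5 − 2 = 34 patients, and 26/34 = 76.5%, which reproduces. The mix of types among those 34 is not given. N = 30 itself cannot be reproduced, because no alpha, power, effect size or precision target is stated.

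**Assumptions.** Even split (15/15 or 25/25), two-sided 5% level, and a contrast of 76.5% v 50% for power.

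**1. What equal observed rates leave open.** The Newcombe interval for p1 − p2 is built from the Wilson limits (l, u) of each proportion. With equal observed rates p its half-width is √[(p − l)² + (u − p)²].
- 11/15 in each type: p = 0.733, Wilson 0.480 to 0.891. √(0.253² + 0.158²) = 0.298, so −30 to +30 points.
- 19/25 in each type: p = 0.760, Wilson 0.566 to 0.885. √(0.194² + 0.125²) = 0.231, so −23 to +23 points.
- Uneven splits with nearly equal rates are similar: 8/10 v 15/20 gives −29 to +31; 13/17 v 25/33 gives −26 to +23.

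**2. What hypothesis 1 needs.** Exact (Clopper-Pearson) 95% limits for one type: 11/15 = 73%, 45% to 92%; 19/25 = 76%, 55% to 91%.

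**3. Power for 76.5% v 50%, idealised.** On a normal scale the shift is d = z(0.765) − z(0.50) = 0.722 SD. Binary power is by exact enumeration; the change score uses the noncentral t with noncentrality d√(n/2).

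| Per type | Fisher | Chi-square | Normal change score |
|---|---|---|---|
| 15 | 18% | 33% | 48% |
| 25 | 40% | 53% | 71% |

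The last column assumes an untruncated normal score, which this design does not produce.

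**4. Power with the stopping rule.** Weekly MADRS was simulated with follow-up ending at the first rating below 10. Assumptions: baseline mean 30, SD 3 to 7, floor 20; SD of proportional improvement 0.2 to 0.4; rating noise SD 2.5; response about 76% v 50%. The adjusted analysis regresses endpoint MADRS on diagnosis and baseline.

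| Per type | Chi-square | Adjusted MADRS |
|---|---|---|
| 15 | about 28–33% | about 37–40% |
| 25 | about 44–51% | about 57–60% |

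Within matched settings the gain is about 6 to 13 points.

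**5. Precision on the MADRS scale.** Half-width = t × SD × √(1 − r²) × √(1/n1 + 1/n2). The documents give neither SD nor r (the correlation with baseline), so SD = 10 is assumed.
- 15/15: 2.048 × 10 × √(2/15) = 7.5 points at r = 0; × √0.75 = 6.5 at r = 0.5.
- 25/25: 2.011 × 10 × √(2/25) = 5.7 points at r = 0; 4.9 at r = 0.5.
- Over SD 8 to 12, the r = 0 figures range over 6.0 to 9.0 and 4.6 to 6.8.

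**The case against.** The strongest reply is that this is a small open-label study, that its numbers are the main limit, and that choosing a linear model over percentages is a matter of preference. Part of that stands: the model does not bring power to 80% at either sample size. But the gain costs nothing to collect, and the plan already calls the measure primary.

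Four stronger readings are tempting and are not supported.

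- **That the plan prescribes raw percentages pooled over sites.** It is silent on both pooling and adjustment. If the 30 patients in Statistical Methods are all from one site, there is no site term to omit. A site effect passing for a diagnosis effect can be constructed. Suppose 30 patients at one site with 80% response and 20% type I, and 20 at the other with 60% and 80%. The result is (6 × 0.8 + 16 × 0.6)/22 = 65.5% for type I v (24 × 0.8 + 4 × 0.6)/28 = 77.1% for type II, with no diagnosis effect. Those site rates and mixes are invented, and the gap's Newcombe interval (about −36 to +13 points) would not show a difference.
- **That hypothesis 1 rests on the types being equal.** It claims effectiveness in each type, so each type's own rate is the relevant evidence. The ±23 to ±30 point interval bears only on the added comparison.
- **That baseline is ignored altogether.** Response is a fall of at least half from the patient's own baseline. What is missing is covariate adjustment.
- **That MADRS change is far more powerful, or that no difference could be seen.** The 15 to 18 point advantage over chi-square in the idealised table (48 − 33 and 71 − 53) shrinks once early stopping is allowed for, and the contrast with Fisher is flattered by that test's conservatism. By normal approximation, gaps of about 50 points (N = 30) or 39 to 41 points (N = 50) would be found with 80% power even on percentages.

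Nor is this the only comparison planned: onset of manic symptoms is also separated by diagnosis, and the hypotheses set remitters against other responders and bipolar against unipolar patients.

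**Conclusion.** The point holds as an inexpensive improvement. It does not threaten the trial's main result. The planned comparison of types is attached to a dichotomised outcome, has no stated interval or adjustment, and leaves unused the score that the protocol names as its primary efficacy measure. Equal observed response rates would leave differences of about 23 to 30 points open either way. A baseline-adjusted MADRS analysis gains about 6 to 13 points of power over chi-square and remains below 80%.

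The interval widths rest on the even split. The power figures rest on the assumed 76.5% v 50% contrast and the simulation inputs above; none of these is given in the documents except 76.5%, which is a completer rate for both types together. At these sample sizes no choice of analysis can establish equal effectiveness. Adjustment for baseline and site would also not remove confounding by the different mood-stabiliser requirements for the two types.

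**What to change.** Amend Statistical Methods, Primary Efficacy Analysis, as follows.

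1. For hypothesis 1, report the response percentage in each type with an exact 95% CI.
2. Compare types by a linear model of endpoint MADRS (or change) on diagnosis with baseline MADRS as covariate, adding site if both sites are analysed. Report the adjusted difference with 95% CI, and beside it the difference in response percentages with a Newcombe 95% CI.
3. Define endpoint for this analysis as the last rating at or before treatment stop, since remitters can finish before 30 sessions. Report how many endpoints come from patients who withdrew.
4. Label the comparison descriptive. State that finding no difference is not evidence of equal effectiveness, and that the types also differ in required mood stabilisation, which the model does not remove.
5. Reconcile the 30 patients in Statistical Methods with the 30 + 20 in Study Population, and say whether both sites enter the analysis.

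The cost is a few sentences and slightly more analysis, on MADRS, diagnosis and site data that the study collects anyway. The covariates use one or two degrees of freedom.
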